### **4. Inclusion and Exclusion Criteria**

#### 4.1. Recruitment of Subjects and Inclusion

Subjects who qualify for inclusion will be those potential subjects identified by [name] being seen at the UNM Pain Clinic who are experiencing pain with "suboptimal" pain relief (defined as discussed below in this section) by standard pain treatment. A randomization table for all subjects receiving pramipexole vs. placebo will be generated such that the Clinical Research Coordinator will use as a template when dispensing drug at the time of consent. All types of chronic pain will be considered, and thus, specific types of chronic pain will not be part of the inclusion or exclusion criteria. Non-English, Spanish speaking subjects will be included. Adults 18 yrs. or older will be included. Women who are not post-menopausal or have not undergone an oophorectomy/hysterectomy will be excluded.

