## *Non-opioid pramipexole suppresses immune NLRP3 reactivity for pain*

Initial screening will occur at the time when [name] is evaluating the patient in the pain clinic. The Electronic Medical Record database is up-to-date and will be viewed at the time of the clinical evaluation. Data that will be evaluated and collected are: sex, weight, height, age, race/ethnicity, years post-menopausal, prior oophorectomy/hysterectomy, years under pain treatment, pain diagnosis (etiology), and type of insurance.

At the time [name] is evaluating a patient that meets the inclusion criteria, 3 standardized questions will be asked:

- (1) Are you happy with the amount of pain relief so far?
- (2) Would you like to try something else to improve your pain relief?
- (3) Are you able to do everything you want to do with the current treatment?

At this time, systemized exclusion criteria will be evaluated as noted in the table below.

Based on the Electronic Medical Record, [name] will have access to information regarding prior history of renal impairment. If [name] suspects the possible presence of renal impairment, a blood panel will be evaluated prior to potential patient participation.

As indicated in the Inclusion/Exclusion Criteria table, Patients with Parkinson's Disease or patients who are taking prescription medications that act as dopamine agonists are excluded from the study.

Note that only those patients who are pregnant will be excluded. A pregnancy test at the time of enrollment and at mid-term (end of 2 weeks of the 4 week study) when subjects check in with the Clinical Research Coordinator. The second pregnancy test will act to mitigate risks of false negative pregnancy test results at the time of enrollment..

4.2. children, a particular racial or ethnic group, etc. and provide justification.

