#### **INCLUSION OF CHILDREN**

This research study will include only individuals 18 years of age and older because chronic pain is rare in pediatric populations. The mechanism underlying its development is not typically expressed until adulthood. Any pediatric chronic pain cases encountered are thus likely to have a substantial idiopathic component. This factor along with the small sample would make results interpretation difficult or impossible for pediatric patients.

“Suboptimal pain relief/ scores” is vague because the Brief Pain Inventory address two discrete aspects of pain: (1) pain severity and (2) pain interference that are subjectively evaluated (Tan, Jensen et al. 2004, Walton, Beattie et al. 2016). The scores obtained from aspects of the scale (items 1-6) that evaluate pain severity and the quality of the pain (burning vs. aching) focuses on current or recent pain. However, the scores obtained from aspects that target affective and physical interference (item 9 with 7 subscales) of pain experience and provides a more complete evaluation of issues surrounding quality of life that are frequently (but not always) considered more critical to patient’s pain experience. Item #8 of the pain scale (“In the past 24 hours, how much pain relief have pain treatments or medications provided? Please circle the percentage that most shows how much relief you have received”) targets the key issue of “suboptimal” pain relief, but only in the past 24 hrs, and provides a “snapshot” of the patient’s chronic pain relief. Therefore, while it may seem to oversimplify the patient’s level of pain relief, patient scores 5 or greater on most items in the Brief Pain Inventory will be considered “suboptimal”.

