### **5. Number of Subjects**

- 5.4. All subjects will be recruited from the UNMH outpatient population from the UNMH Pain Center.
- 5.5. The target sample size is 30 subjects with complete data. The investigators may recruit up to 45 patients to allow for any dropouts.
- 5.6. All subject recruited will participate. There will be no screening after recruitment.

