## **9. Resources Available**

- 9.4. The PI and study staff have received training for clinical trials. [name] (PhD) is a basic scientist conducting the cell assays and interpreting the data results. [name](PhD) is a basic scientist directing the CTSC core for conducting the cell assays and interpreting the resultant data. [name] (PhD) is a statistician and familiar with clinical trials designs, and [name] (MD) is a physician who specialized in pain treatment at the UNMH Pain Clinic.
- 9.5. [name], MD will be responsible for medical decision-making and ordering and evaluation of necessary diagnostics and therapeutics.
- 9.6. [name] treats 15-30 patients daily at the UNMH Pain Clinic. With this high access to patients, the goal of enrolling 30 patients during an 11 month period is predicted to be very feasible.

All 30 recruited patients will be needed with no further screening.

An estimated 6 hrs per patient will be devoted to consent, completing surveys, blood draw, scheduling and dispensing the pramipexole or placebo by the Clinical Research Coordinator.

- The facilities used will be at the CTSC where consent, enrollment, scheduling visits, obtaining blood samples, completion of the Brief Pain Inventory survey, dispensing drugs at initiation and at midterm (end of week 2,) and collecting unused drug at termination. For the biological assays from human cell lines or from blood samples, the clinical laboratory arm of the CTSC, Center for Molecular Drug Discovery, will be used.
- The availability of medical and/or psychological resources that subjects might need as a result of an anticipated consequences of the human research will be available by [name] or by referral from [name]. The anticipated consequences of the research will be (1) improved pain relief, (2) no change in pain relief, or (3) a worsening of pain. [name] will continue to monitor patients after the study is terminated, as these patients will continue to receive outpatient care from the pain clinic.

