## **12. Study Procedures**

The goal of Phase II will be to determine the therapeutic benefit of pramipexole for pain, which is a repurposing of this FDA-approved drug with a good safety profile. In collaboration with [name] (co-I at UNMH Pain Clinic), patients from the UNM pain clinic will be recruited who are experiencing modest or suboptimal pain relief. The patient will meet the CTSC Clinical Research Coordinator, who will escort the patient to the Clinical Research Lab. At the time, an explanation of the study, consent, the Brief Pain Inventory survey will be completed, blood draw and Clinocard will be given to the patient (\$15/visit). Scheduling for the midterm visit to the CTSC (at the end of two weeks) will be determined. At the time of consent, all patients will be under standard pain treatment and will be randomized into two groups: (1) patients receiving pramipexole in addition to their standard ongoing pain treatment, or (2) no pramipexole but will continue to receive the standard pain treatment. Patients will be followed up in the morning at weekly intervals to provide pain scores either by phone (for week 1 and 3), or by return visit (for end of week 2 and at the end of week 4) until study termination which is at the end of week 4.. At the initiation of the study and at the end of 4 weeks, blood will be collected and analyzed for mRNA for TLR4, p38, NFKB, NLRP3-ASC, Caspase-1, IL-1 $\beta$ , TNF- $\alpha$ , HMGB1, and IL-10. The dose and route of administration of pramipexole will be identical to that previously approved for the treatment of Restless Legs Syndrome and according to manufacturer's recommended prescribing protocol (Mirapex, Boehringer Ingelheim Int. GmbH). Briefly, oral dosage will be titrated each week to achieve a weekly total daily dose of 0.125 (mg), 0.250, 0.5 or 0.750. Patients will take one capsule containing pramipexole or placebo 2-3 hours before bedtime.

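### Nothing visible in the plan applies its own BPI eligibility threshold before randomisation, so patients below that threshold can be randomised

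*Combined protocol and SAP*

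**What the plan says.** Section 4.1 admits patients with suboptimal "pain relief (defined as discussed below in this section) by standard pain treatment". The definition comes at the end of Section 4, under the heading on inclusion of children: "patient scores 5 or greater on most items in the Brief Pain Inventory will be considered" suboptimal. The threshold is therefore part of the inclusion criterion and not background.

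Section 4 also describes the screen in the pain clinic. It consists of a record review, which runs from demographics to "years under pain treatment, pain diagnosis (etiology), and type of insurance", and a short interview in which "3 standardized questions will be asked". These cover satisfaction with relief, interest in trying something else, and ability to do what the patient wants. The exclusion criteria are checked at the same time. No BPI or other pain score is listed.

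Section 12 gives the order at the first CTSC visit: "an explanation of the study, consent, the Brief Pain Inventory survey will be completed, blood draw". Section 8.4 has the coordinator, not the clinic physician, collect the BPI. Sections 12 and 13 place randomisation at consent. Sections 4.1, 14 (recruitment paragraph) and 19 have the coordinator use the randomisation table to dispense drug at consent.

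Section 5.6 says that everyone recruited takes part and adds "There will be no screening after recruitment". Section 9.6 says "All 30 recruited patients will be needed with no further screening".

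**The concern.** An eligibility threshold works only if it is measured before the patient is committed to the trial and if a patient who misses it can be turned away. On the visible text neither condition is met. The measurement first appears after consent, at the step where patients are also randomised and given drug, and the plan says nobody is screened out from then on. No section says what happens to a consented patient who scores below the threshold.

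Two things are at stake. Patients outside the plan's stated criterion could receive study medication. And the BPI is the primary endpoint (Section 7.4) in a trial aiming for 30 patients with complete data, so patients with little pain to lose could shrink the observed difference between arms. Section 12 describes improved control as a fall of 3 points on the BPI, which a patient starting below 3 cannot reach.

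**Working it through.** **Order of steps.** The passages set side by side:

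| Step | Where stated | Can the BPI threshold be applied here? |
|---|---|---|
| Clinic screen: records, three questions, exclusions | Section 4 | No; no BPI listed |
| Consent | Section 12 | No; BPI listed after it |
| First BPI | Sections 8.4 and 12 | Yes, if a patient could then be declined |
| Randomisation | Sections 12 and 13: at consent | Order relative to scoring the BPI not stated |
| Dispensing | Sections 4.1, 14 and 19: at consent | Same |
| After recruitment | Sections 5.6 and 9.6 | No; further screening ruled out |

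**Is there a separate screening form?** Section 12 gives five BPI surveys per patient and weekly scores for four weeks. 1 baseline + 4 weekly = 5. The count leaves no sixth form for an earlier clinic screen.

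**How many patients could be affected?** The documents give no baseline BPI distribution and no share below the threshold, so this cannot be calculated for this trial. As an assumption, let *f* be the share of referred patients below it. The expected number in 30 is 30*f*, and the chance of at least one is 1 − (1 − *f*)^30.

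| Assumed *f* | Expected in 30 | Chance of at least one |
|---|---|---|
| 5% | 1.5 | 1 − 0.95^30 = 79% |
| 10% | 3 | 1 − 0.90^30 = 96% |
| 20% | 6 | 1 − 0.80^30 = 99.9% |

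**What could dilution cost?** The plan gives no SD, alpha, power or target difference for the sample size, so there is no figure of its own to reproduce. For illustration, assume 15 per arm, two-sided alpha 0.05, a true difference of 3 points in patients who meet the threshold, no effect in those who do not, and an SD unchanged by the mix. The average difference becomes 3(1 − *f*). By normal approximation, power = Φ(3(1 − *f*) / (SD × √(2/15)) − 1.96), with √(2/15) = 0.365.

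| Assumed *f* | Difference | Power, SD 2 | Power, SD 3 |
|---|---|---|---|
| 0% | 3.0 | Φ(4.108 − 1.96) = 98% | Φ(2.739 − 1.96) = 78% |
| 10% | 2.7 | 96% | 69% |
| 20% | 2.4 | Φ(3.286 − 1.96) = 91% | Φ(2.191 − 1.96) = 59% |

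The assumption of no effect below the threshold is severe, so these losses are towards the upper end for each *f*.

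**Can the rule be scored as written?** The number of items that makes up *most* is not defined. By Section 4's own description, item 8 is the percentage of relief obtained, so a high value means good relief. That runs opposite to the severity and interference items, and a cut-off of 5 does not fit a percentage. Two coordinators could classify the same patient differently.

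**The case against.** The best defence is that *recruited* means already qualified. Sections 14 and 19 say that it is those who qualify for inclusion who are recruited, and Section 4.1 has the pain physician identify them. On that reading, Section 5.6 only says that nobody is screened twice. This does not settle the matter. The qualifying rule is a BPI score, and no visible section schedules a BPI before consent. The three clinic questions are not a substitute, because a patient may be dissatisfied and still score below 5 on most items.

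Several counterpoints stand. The inclusion/exclusion table that Section 4 mentions and Figure 4 are missing from the available text; either might place a BPI earlier, although it would then have to be squared with the order in Section 12. Section 12 lists the BPI at the first visit, and nothing says drug is handed over before the form is seen, so the threshold could be applied in practice. Some checks do occur at entry: a pregnancy test at enrolment and, where renal impairment is suspected, a blood panel before participation. Neither tests the BPI threshold.

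A reader might infer that a large block of ineligible patients will be randomised. For example, a normal baseline score with mean 5.5 and SD 2 puts 40% below 5 (z = −0.25), or 12 of 30; mean 6.5 and SD 1.5 puts 16% below (z = −1), or about 5. The documents do not support this. Those means and SDs are assumed, the rule concerns most items and not one score, and physician selection and the three questions probably favour higher scores.

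A reader might also infer that every patient below the threshold is unable to improve by 3 points. That is true only below 3. On the same two assumed distributions those are 11% (z = −1.25) and 1% (z = −2.33), or about 3 and 0.3 of 30. The 3-point fall is also an individual titration goal in Section 12, not a responder endpoint in Section 7.

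**Conclusion.** The point holds in limited form. On the visible text the plan's BPI threshold has no step at which it operates, and the no-screening statements remove the obvious one. Patients below it can be randomised; it is not shown that they will be, or how many. Their number is unknown, and the 5% to 20% range above is illustrative.

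Such patients would be allocated at random to both arms, so the consequence is possible dilution and loss of power, not bias in the comparison. Under the stated assumptions, 20% below the threshold would lower power from 98% to 91% (SD 2) or from 78% to 59% (SD 3). The conclusion about the order of steps rests on the text alone, with the reservation that the missing table and figure might add a step. The plan should be corrected, because the conflict touches the main inclusion criterion and the form needed to resolve it is already collected.

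**What to change.** Keep the baseline BPI at the first CTSC visit, and state that it is scored after consent and before randomisation and dispensing. Randomise only patients who meet the Section 4 threshold. Record the others as screen failures who do not count toward the 30 with complete data or the 45 recruited.

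Replace the no-screening statements in Sections 5.6 and 9.6 to match. Changing those two alone is not enough: the consent-time randomisation wording in Sections 12 and 13 and the consent-time dispensing wording in Sections 4.1, 14 and 19 must be moved to after scoring.

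In Section 4, list the BPI items that count, state how many must reach 5, and either leave out item 8 or reverse it on a stated scale. Name who does the scoring.

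The cost is protocol wording, a short scoring rule and a revised order of steps at a visit that already includes the form. Some consented patients will become screen failures, and enrolment may be slightly slower.

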### **6. Study Timelines**

#### *6.4. Describe:*

- The duration the subject will participate in the study is 4 weeks
- The duration anticipated to enroll all subjects may require 10-11 months
- The expected duration for the investigators to complete the study analyses will be 12 months, with most of the analysis occurring in the final months 11-12.

## **7. Study Endpoints**

- 7.4. The primary endpoint is the paper-and-pencil survey, the Brief Pain Inventory. The secondary study endpoints will be mRNA and protein analysis from blood samples provided at the initiation and terminal of the study.
- 7.5. *Safety endpoints of the study will include the following: (1) Worsening of pain score or increased verbal dissatisfaction with pain relief, (2) sudden onset of sleep without warning, (3) intense urges, (4) hallucinations and/or psychotic-like behaviors, (5) fever, and (6) orthostatic hypotension. While the patients who experience these adverse events, dosing with pramipexole will require a 50% step-wise reduction over a period of two weeks. Given the maximal allowable dose is 0.75 mg, this prescribed step-wise reduction is well within the manufacturer's recommended tapering of pramipexole, which the recommended dose reduction is 0.375 per day.*
- 7.6. No exploratory endpoint are in the current study.

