**Dose escalation risks**

Dose titration will increase by double if efficacy has not been achieved by the end of one week at the lower initial dose. A dose of 0.125 mg pramipexole once per night for 1 week is initiated for all subjects. At the end of week one, subjects will either increase the dose by double, 0.25 mg if pain relief is not satisfactory, or will remain at 0.125 mg if relief is satisfactory. A 2nd titration may occur at the end of week 2, with the dose escalating from 0.25 mg to 0.75 mg per night. Please see flow chart indicating the 'Dispensing Guideline', as an illustration.

Safety will be monitored either at the time the CRC asks the subject to provide their scores on the Brief Pain Inventory, or when the subject calls [name] reporting adverse experiences as indicated in safety endpoints. Upon consent, subjects will be instructed to call [name] should any adverse experiences noted in the 'safety endpoints' occur during the study period. After the study period is terminated, subjects will continue to see [name] in follow-up visits as needed.

All risks associated with pramipexole (Mirapex; Boehringer Ingelheim Pharmaceuticals) according to the manufacturer are:

1. Falling asleep during activities of daily living. Sudden onset of sleep may occur without warning. Somnolence is a common occurrence in patients receiving pramipexole at doses above 1.5 mg/day (0.5 mg three times a day). In controlled clinical trials in Restless Leg Syndrome, patients treated with MIRAPEX tablets at doses of 0.25-0.75 mg once a day, the incidence of somnolence was 6% compared to an incidence of 3% for placebo-treated patients.

2. Symptomatic orthostatic hypotension: Dopamine agonists, in clinical studies and clinical experience, appear to impair the systemic regulation of blood pressure, with resulting orthostatic hypotension, especially during dose escalation. Despite clear orthostatic effects in normal volunteers, the reported incidence of clinically significant orthostatic hypotension was not greater among those assigned to pramipexole tablets than among those assigned to placebo.

Symptomatic orthostatic hypotension will be monitored during dose escalation during weeks 1-2, as well as throughout the 4-week study. Monitoring will occur as detailed in “Collection and Reporting of Adverse Events”.

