3. Impulse control/Compulsive behaviors: Patients may experience compulsive behaviors and other intense urges taking one or more of the medications, including pramipexole, that increase central dopaminergic tone and that are generally used for the treatment of Parkinson’s disease. For this reason, Parkinson’s Disease patients are not included in this study. However, if patients or their caregivers experience increased gambling urges, sexual urges, uncontrolled spending or other urges while being treated with pramipexole, subjects will be asked to report this to [name] and/or the CRC. [name] will consider dose reduction.
4. Hallucinations and Psychotic-like Behavior: The following symptoms are associated with patients with Parkinson’s Disease. In the three double-blind, placebo-controlled trials in early Parkinson's disease, hallucinations were observed in 9% (35 of 388) of patients receiving pramipexole tablets, compared with 2.6% (6 of 235) of patients receiving placebo.

Patients with a major psychotic disorder should ordinarily not be treated with dopamine agonists, including pramipexole, because of the risk of exacerbating the psychosis. In addition, certain medications used to treat psychosis may exacerbate the symptoms of Parkinson’s disease and may decrease the effectiveness of pramipexole. If a subject experiences hallucinations while taking pramipexole, pramipexole will be discontinued or reduced step-wise, pending the dose.

5. Dyskinesia: May be caused or exacerbated by pramipexole.
6. Renal impairment: Since pramipexole is eliminated through the kidneys, caution will be exercised in the current study.
7. Rhabdomyolysis, a condition in which the skeletal muscle rapidly breaks down leading to muscle pains, weakness, vomiting and confusion. A single case of rhabdomyolysis occurred in a 49-year-old male with advanced Parkinson's disease treated with Pramipexole tablets. The patient was hospitalized. The symptoms resolved with discontinuation of the medication.
8. Events reported with dopaminergic therapy: Include hyperpyrexia and confusion, fibrotic complications, and melanoma.

Most common adverse reactions (incidence >5% and greater than placebo):

1. Early PD without levodopa: nausea, dizziness, somnolence, insomnia, constipation, asthenia, and hallucinations.

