## **15. Withdrawal of Subjects**

Anticipated circumstances where subjects may be withdrawn from the research without their consent may be if their pain scores worsen for longer than a week.

In the event of early withdrawal, patients will be tapered from 0.5 (if currently taking that dosage) to 0.250 for 1 week. However, according to the manufacturer's (Boehringer Ingelheim, Inc) packet information, pramipexole at doses of up to 0.75 once daily can be discontinued without taper.

While there are no contraindications associated with pramipexole, the collection and reporting of adverse are as follows:

The collection and reporting of adverse events will occur at: (1) the time of the phone conversation at the end of weeks 1 and 3 with the CRC who will collect the Brief Pain Inventory scores, (2) at the end of week 2, the time of the mid-term in-person meeting with the CRC when the subject will provide the scores of the BPI for that week and will pick up drug dispense #2, (3) At the final in-person with the CRC, at the termination of the study at week 4, and (4) at any point during the study when the subject calls the CRC to report an adverse event or when the subject calls [name]. All adverse events will be recorded by the CRC and kept with the subject's study records.

See actions upon evidence of symptomatic orthostatic hypotension above (Section 14, "Provisions to monitor the data to ensure the safety of subjects"), and other adverse

reactions will be monitored during dose escalation during weeks 1-2, as well as throughout the 4-week study. Monitored will occur as detailed in “Collection and Reporting of Adverse Events”.

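### Section 7.5 makes a two-week dose reduction mandatory after any of six safety events, which conflicts with the Section 14 rules for hallucinations, urges and unsatisfactory pain relief

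*Combined protocol and SAP*

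**What the plan says.** Section 7.5 names six safety events: worse pain or more dissatisfaction, sudden sleep, intense urges, hallucinations or psychotic-like behaviour, fever, and orthostatic hypotension. The first reads "Worsening of pain score or increased verbal dissatisfaction with pain relief". For patients with these events, "dosing with pramipexole will require a 50% step-wise reduction over a period of two weeks". The sentence makes no distinction by event, severity or dose, and does not mention stopping.

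Section 14, under Dose escalation risks, gives different actions for some of the same events:

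- Hallucinations: "pramipexole will be discontinued or reduced step-wise, pending the dose".
- Urges: the physician "will consider dose reduction".
- Pain relief at the end of week 1: "subjects will either increase the dose by double, 0.25 mg if pain relief is not satisfactory"; otherwise the dose stays at 0.125 mg. A second upward step may follow at the end of week 2.

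Section 15 says that a subject may be withdrawn "if their pain scores worsen for longer than a week". It gives a one-week taper from 0.5 mg to 0.25 mg at early withdrawal and reports from the manufacturer that "pramipexole at doses of up to 0.75 once daily can be discontinued without taper". For orthostatic hypotension it refers the reader to actions in Section 14.

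**The concern.** Section 7.5 is worded as a requirement, while Section 14 leaves the choice open or points the other way. For hallucinations and urges, a mandatory reduction stands beside a permission to stop and a mere consideration of reducing. For pain, a subject who has got worse is to have the dose cut under one section and raised under another.

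What is at stake is subject safety and consistent dosing. The coordinator makes the weekly contacts and collects both the adverse events and the Brief Pain Inventory (BPI) scores. Two staff members reading different sections could handle the same event differently. The pain item also ties the dose rule to the BPI, which is the primary endpoint, in a trial that aims for 30 complete subjects.

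**Working it through.** **The plan's own figure.** Section 7.5 gives a maximum dose of 0.75 mg and a manufacturer's reduction of 0.375 per day. Half of the maximum is 0.75 × 0.5 = 0.375, so the two figures agree. The problem lies in the rules, not in the arithmetic.

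**The rules side by side.**

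| Section 7.5 event | Section 7.5 | Section 14 | Section 15 | Result |
|---|---|---|---|---|
| 1. Worse pain or more dissatisfaction | Reduce | Double the dose at end of week 1 if relief is unsatisfactory | Possible withdrawal if worse for over a week | Opposite directions |
| 2. Sudden sleep | Reduce | Risk described, no dose action | Nothing specific | 7.5 is the only event-specific dose rule |
| 3. Urges | Reduce | Consider reducing | Nothing specific | Mandatory against discretionary |
| 4. Hallucinations | Reduce | Stop or reduce, depending on dose | Nothing specific | Stopping allowed in 14, absent from 7.5 |
| 5. Fever | Reduce | No dose action | Nothing specific | 7.5 is the only event-specific dose rule |
| 6. Orthostatic hypotension | Reduce | Monitoring and reporting only | Refers to actions in 14 | Cross-reference leads to no action |

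Count: events 1, 3 and 4 have conflicting rules (3 of 6). Event 6 has an empty cross-reference (1 of 6). Events 2 and 5 have no competing event-specific rule (2 of 6). 3 + 1 + 2 = 6.

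**Who meets both pain rules.** Section 12 sets the treatment goal at a BPI score 3 points lower. Two assumptions are needed: that unsatisfactory relief means missing this goal, and that worsening is judged against the starting score. Let the change be the week 1 score minus the starting score.

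- Change of −3 or lower: goal met, dose stays, Section 7.5 not triggered by the score.
- Change above −3 and up to 0: titration raises the dose. Section 7.5 is not triggered by the score, only by increased dissatisfaction.
- Change above 0: titration raises the dose and Section 7.5 requires a reduction.

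The overlap is therefore subjects who get worse or become more dissatisfied. Section 15 needs worsening for longer than a week, so it adds a third possible outcome later.

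**Order of precedence.** Sections 7, 12, 14, 15 and 31 contain no statement that ranks these rules.

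**The case against.** The strongest reply is that nobody is bound to keep a subject on drug. Section 9.5 gives the physician responsibility for medical decisions. Section 24 lets the investigators end participation in the subject's best interest, and subjects may withdraw at any time. This stands, and it limits the harm. A reader might infer that a subject with hallucinations or sudden sleep would be held on drug for two more weeks. The documents do not support that: the general power to stop covers every event, and Section 14 has its own rule for hallucinations. The power to stop does not, however, reconcile the wording of Section 7.5 with Section 14.

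Second, the Section 7.5 sentence is grammatically broken and goes on to compare the step with the manufacturer's tapering, so it may mean a gradual step-down towards stopping. That is possible, but it still makes the two-week course a requirement. The dose condition in the hallucination rule does not remove the conflict either, because Section 7.5 has no dose exception.

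Third, worsening is not the same as unsatisfactory relief; Section 9 itself separates no change from worse pain. This is right. A reader might infer that every unsatisfied subject is caught by both rules, but only those who get worse or more dissatisfied are.

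Fourth, a reader might take the no-taper statement in Section 15, or the instruction to taper or stop in one Section 14 suspension case, as contradicting Section 7.5. Neither does. A cautious taper is compatible with a label that does not require one, and the suspension case concerns unanticipated risk, not a listed event in one subject.

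Finally, Section 14 cites a dispensing flow chart and an adverse-event script that are not clearly in the available text. Either might state a precedence, so the finding is limited to the visible text.

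**Conclusion.** The conflict is real but narrow. Section 7.5 makes mandatory what Section 14 leaves to judgement for hallucinations and urges. It also runs against the titration rule for subjects whose pain worsens or whose dissatisfaction increases. Section 15 refers to orthostatic hypotension actions that Section 14 does not contain.

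The size is three of six events with conflicting rules and one with an empty cross-reference. The documents give no expected frequency for these events in this population, so the number of subjects affected cannot be estimated. No error rate or sample size changes.

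A reader might try to express the harm as extra milligrams taken, as a ratio between the two directed doses, or as a reduction running past week 4. Those figures are not sound evidence of magnitude. They need a halve-and-hold schedule that Section 7.5 does not define, a dose the capsules cannot supply, or the separate discrepancy over the size of the second titration step.

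The conclusion assumes that the broken sentence in Section 7.5 refers to the six events listed just before it, which is the only natural reading.

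**What to change.** Replace the dosing sentence in Section 7.5 with one rule for study capsules, the same in both arms, and have Sections 14 and 15 refer to it.

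- **Events 2 to 6.** The medical investigator may reduce by whole capsules or stop at once at any dose up to 0.75 mg. No two-week reduction is required. First confirm the no-taper statement in Section 15 against the attached package insert.
- **Event 1.** Worse pain or dissatisfaction does not trigger a mandatory reduction. Dissatisfaction alone follows the Section 14 titration. A worse pain score is reviewed by the medical investigator before any increase, and Section 15 applies after a week.
- **Orthostatic hypotension.** Name this rule as the action to which Section 15 refers.

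Whether a given event should lead to stopping or to a step-down by default is a clinical choice that the documents do not settle, and it should stay with the medical investigator.

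The cost is protocol wording. The downside is that some subjects may stop capsules earlier, so their weekly BPI scores should still be collected to week 4.
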